- 60. White, A., *Measuring Pain.* Acupuncture in Medicine, 1998. **16**(2): p. 1.

15. Appendix 2 – Diabetic Foot Ulcer Scale – Short Form

Diabetic Foot Ulcer Scale - Short Form

INSTRUCTIONS:

These questions ask about the effect foot ulcers may have on your daily life and well-being. Please read each question carefully and think about the effect of your foot ulcers.

Answer every question by circling one number on each line. If you are unsure about how to answer a question, please give the best answer you can.

Diabetic Foot Ulcer - Short Form

1. How much have your foot ulcers:						
		A little bit	Moder- ately		A great deal	
a) stopped you from doing the hobbies and recreational activities that you enjoy	1	2	3	4	5	
b) changed the kinds of hobbies and recreational activities that you enjoy doing	1	2	3	4	5	
c) stopped you from going away for a weekend, vacation, or holiday	1	2	3	4	5	
d) made you choose a different kind of weekend, vacation, or holiday than you would have preferred	1	2	3	4	5	
e) meant you had to spend more time planning and organizing leisure activities	1	2	3	4	5	

2. Because of your foot ulcers, how often have you felt: None of the A little of Some of the Most of the All of the the time time time time time 3 a) fatigued or tired 1 2 5 4 b) drained 2 3 4 c) that you had 5 3 4 difficulty sleeping d) pain while walking 3 5 or standing e) pain during the 3 night

3. Because of your foot ulcers, how often have you: A little All of None of Some of Most of the time the time the time time a) had to depend on others to help you look after yourself (like 3 5 washing and dressing) b) had to depend on others to do household chores (like cooking, 1 3 5 cleaning or laundry) c) had to depend on others for 1 3 2 5 getting out of the house d) had to spend more time planning or organizing your daily 5 life e) felt that doing anything took 3 5 longer than you would have liked

4. Because of your foot ulcers, have you felt:							
	Not at all	Slightly		Quite a bit	Extre- mely		
a) angry that you were not able to do what you wanted	1	2	3	4	5		
b) frustrated by others doing things for you when you would rather do them yourself	1	2	3	4	5		
c) frustrated because you were not able to do what you wanted	1	2	3	4	5		
d) worried your ulcer(s) will never heal	1	2	3	4	5		
e) worried you may have to have an amputation	1	2	3	4	5		
f) worried about injury to your feet	1	2	3	4	5		
g) depressed that you were not able to do what you wanted	1	2	3	4	5		
h) worried about getting ulcers in the future	1	2	3	4	5		
i) angry this has happened to you	1	2	3	4	5		

j) frustrated because you have difficulty getting around	1	2	3	4	5			
5. Because of your foot ulcers, how often were you bothered by:								
	None of the time	A little of the time	the time	of the	All of the time			
a) having to keep weight off your foot ulcer	1	2	3	4	5			
b) the amount of time involved in caring for your foot ulcer (including dressing changes, waiting for the home health care nurse, and keeping the ulcer clean)	1	2	3	4	5			
c) the appearance, odor or weeping of your ulcer	1	2	3	4	5			
d) having to depend on others to help care for your foot ulcer	1	2	3	4	5			

THANK YOU FOR COMPLETING THIS QUESTIONNAIRE

DFS-SF © 1999 Mapi Research Trust, All rights reserved

DFS-SF - United States/English - Version of 22 Feb 08 - Mapi Research Institute. ID4557 / DFS-SFeng-USq_author

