Appendix 2 – Diabetic Foot Ulcer Scale – Short	
	Quality Control and Quality Assurance. Training

Celliant Clinical Trial Protocol
PI: [name]
Protocol #: HGX2020-01

Primary Study Contacts

UT Southwestern Medical Center, Department of Plastic Surgery

Principal Investigator	[name]
email	[contact]
[contact]

Parkland Hospital, Department of Plastic Surgery

Principal Investigator	[name]
email	[contact]
[contact]

Executive Summary

Title of Study Study to Evaluate Celliant Diabetic Medical Socks to Increase Tissue Oxygenation

and Incidence of Complete Wound Closure in Diabetic Foot Wounds

Protocol Number HGX2020-01

Study Purpose The purpose of this study is to demonstrate that the use of Celliant Socks

increases tissue oxygenation (via oxygen saturation, StO₂) and incidence of wound closure in subjects with diabetic foot ulcers. This study will use hyperspectral imaging and wound assessment to measure these outcomes.

Study Design This study is a prospective, multicenter, double-blind, 1:1 randomized clinical trial.

Enrollment The study will enroll 254 evaluable subjects total, 127 per arm to meet the Primary

Endpoint. Enrollment may continue up to twenty-five hundred (2500) evaluable subjects total to meet the Key Secondary Endpoint of complete wound closure.

Investigational UT Southwestern, Department of Plastic Surgery Sites Parkland Hospital, Department of Plastic Surgery

Study Duration Up to 28 weeks (including run-in and followup phase)

Efficacy EndpointsPrimary Endpoint: To compare the percent change from baseline in tissue oxygenation in Celliant and Control treated groups 12 weeks post initial application,

as measured by hyperspectral imaging.

Key Secondary Endpoint: To compare the incidence of complete wound closure of Celliant and Control treated groups 12 weeks post initial application.

Other Secondary Endpoints:

 Change in pain assessment as reported using the Visual Analog Scale (VAS)

- 2. 3-month follow-up to assess wound closure and reoccurrence
- 3. Accelerated wound closure as measured by changes in wound area, depth and volume.
- 4. Assessment of Compliance
- 5. Outcomes of Diabetic Foot Ulcer Scale Short Form
- 6. Study related AE/SAEs

Safety Endpoints The incidence of events reported

Study Groups

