- 8. Perform SPP and tcPO2 measurements at Visit 4 (maybe be taken instead at visit 5 or 6 if subject has not been wearing their treatment sock leading up to the visit or misses this visit).
- 9. Collect all relevant concomitant medication
- 10. Perform pain assessment.
- 11. Redress the wound with standard of care (if wound is still active) and apply Celliant Active or Control Sock and apply offloading (if indicated).
- 12. Wound will be offloaded.
- 13. Provide subject with any additional medical socks needed until the next visit. Instruct the subject to change the socks if they become wet, soiled, or bloody and under any conditions dictated by PI instructions. Instruct the subject that they must wear the sock at all times and that including the 3 hours leading up to the next study visit.

Study Visit - Wound Closed

- 1. The study wound is defined as closed when there is complete skin re-epithelialization without drainage or dressing requirements confirmed by the evaluating physician at 2 consecutive study visits 2 weeks apart.
- 2. At this visit the subject will perform the EOS evaluation and enter the follow-up phase of the study.

Study Visit 12/EOS

- 1. If the study wound closes prior to the 12-week study mark, subjects will perform EOS visit at the time of wound closure. See Study Visit Wound Closed.
- 2. A subject whose wound does not close completely by week 12 will exited from the study after the week 12 wound evaluation.
- 3. Document study compliance information from the subject
 - a. Amount of time the sock was worn throughout the week
 - b. Was it worn during the day/night?
 - c. When/why the sock was changed.

- d. Has the sock been on in the 3 hours leading up to the appointment?
- 4. Remove sock and dressing and immediately perform hyperspectral imaging of the dorsal and plantar aspects of the foot if wound is active or closed.
- 5. Assess target ulcer (if wound has closed, document as such, perform steps 7-12 and skip to Study Visit Wound Closed).
- 6. If the subject still has a large enough wound, collect 4 tissue samples. Two in RNA later and two in DNA/RNA shield.
- 7. Perform standardized photography of the study wound.
- 8. Assess the ulcer area (cm²), perimeter (cm), and greatest depth (cm) using the inSight device.
- 9. Perform SPP if wound is active or closed.
- 10. Perform tcpO2 if wound is active or closed.
- 11. Perform pain assessment
- 12. Ask the subject if they thought they were in the active or control group

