- 13. Administer DFS-SF
- 14. Collect all relevant concomitant medication
- 15. Redress the wound per physician-directed standard of care.

Study Visit Follow up

- 1. If the subject's wound closes within the 12-week treatment window, they will enter the follow up phase of the study.
- 2. At 3 months post closure, wound evaluation will be performed as outlined below. This follow-up visit will be in person. In the event that an in-person visit is not possible, a telehealth visit may be performed and documented as such.
 - a. Assess the study wound to determine that it remained closed
 - b. If the study wound has reoccurred
 - i. record the date of reoccurrence
 - ii. measure the size of dehiscence or re-ulceration
 - iii. exit the subject from the follow up phase
 - c. Assess the study foot for new sites of ulceration
 - i. record the date of reoccurrence
 - ii. measure the size of dehiscence or re-ulceration
 - iii. exit the subject from the follow up phase

Detailed Study Operations

Medical Status/History

• The New York Heart Association (NYHA) Functional Classification System: This system will be used to classify stage of heart failure. The New York Heart Association (NYHA) functional classification system is used to classify the stage of heart failure from Class I to IV (as shown in the table below). This system relates symptoms to everyday activities and the patient's quality of life.

Class	Patient Symptoms
Class I (Mild)	No limitation of physical activity. Ordinary physical activity does not cause undue fatigue, palpitation, or dyspnea (shortness of breath).
Class II (Mild)	Slight limitation of physical activity. Comfortable at rest, but ordinary physical activity results in fatigue, palpitation, or dyspnea.
Class III (Moderate)	Marked limitation of physical activity. Comfortable at rest, but less than ordinary activity causes fatigue, palpitation, or dyspnea.
Class IV (Severe	Unable to carry out any physical activity without discomfort. Symptoms of cardiac insufficiency at rest. If any physical activity is undertaken, discomfort is increased.

- Body Mass Index (BMI): BMI is calculated as the ratio of body weight in kilograms (kg) to height in meters squared (m²).
- Medical History: The following information will be collected from each subject
 - previous ulcer history
 - amputation history
 - lower extremity bypass
 - lower extremity angioplasty
 - coronary artery bypass surgery
 - cardiac angioplasty
 - arthritis
 - liver disease

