The VAS is the most commonly used scale for assessing pain [60]. The VAS is a simple scale that consists of a 10cm line anchored at one end by a label that indicates total absence of the measure being evaluated and at the other end by a label that indicates the worse imaginable presence of the measure being evaluated. The subject marks on the line the spot for the intensity of the measure, which is then measured using a ruler (in mm units).

Infection Evaluation

The following clinical indicators of significant bacterial infection will be recorded as present or absent for the study wound. 'Significant Bacterial Infection Clinical Indicators' are defined in this study as those presenting as excessive beyond which would typically be expected given the clinical condition and nature of the wound type.

- local heat
- spreading redness
- swelling
- increased purulent exudate (draining pus)
- odor
- cellulitis
- loss of function
- fevers
- chills

Sock Use Instructions

The subjects will be provided with 10 pairs of socks on the initial visit and instructed that the socks may be washed as normal laundry as needed (bleach or no bleach). Subjects will be supplied additional pairs as needed on a case by case basis. The sock change frequency will be dictated by the physician; however, the subject will be instructed to change the sock as with any other sock if it becomes wet, soiled, or bloody.

Patient Reported Outcomes

The Diabetic Foot Ulcer Scale – Short Form (DFS-SF) (Appendix B) will be used to collect patient reported outcomes in this trial. The DFS questionnaire is designed to assess the impact of foot ulcers and their treatment on quality of life in people with diabetes.

Excluded Medications/Treatments

During the study procedures, the study subjects will refrain from using hyperbaric oxygen therapy (HBOT) and any cellular or tissue-based products (RegranX etc).

Standard of Care

- All study wounds will be debrided per physician discretion and documented.
- Wound Dressing: Two wound care treatments will be available, depending on wound status and physician discretion

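### The Study Visit 12/EOS list puts the arm-guess question directly before the DFS-SF, so the self-rated quality-of-life score is listed to follow a stated treatment belief; swapping the two steps costs nothing

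*Combined protocol and SAP*

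**What the plan says.** The evidence is in section 3, Study Visit 12/EOS. The last part of that numbered list runs as follows:

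- Step 11: "Perform pain assessment" (the VAS).
- Step 12: "Ask the subject if they thought they were in the active or control group".
- Step 13: "Administer DFS-SF".

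Step 5 of the same list directs subjects whose wound is found closed: "if wound has closed, document as such, perform steps 7-12 and skip to Study Visit Wound Closed". The entry for Study Visit - Wound Closed then says: "At this visit the subject will perform the EOS evaluation and enter the follow-up phase of the study".

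The Executive Summary lists "Outcomes of Diabetic Foot Ulcer Scale Short Form" among the other secondary endpoints. The section on Patient Reported Outcomes says that the DFS-SF "will be used to collect patient reported outcomes in this trial". In the Schedule of Events Table the DFS-SF is marked only in the EOS column. The arm guess has no row there, so the numbered list alone fixes its position.

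The appendix reproduces the questionnaire, which opens "These questions ask about the effect foot ulcers may have on your daily life and well-being". This shows what kind of instrument it is. It says nothing about when in the visit it is given.

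**The concern.** Every DFS-SF item is a self-rating of things such as anger, worry, low mood, fatigue, pain and dependence on others. Such answers can be coloured by what a subject believes about their treatment. Asking for that belief just beforehand brings it to mind at the point where it can do most harm.

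Belief could differ between arms in two ways. Subjects see their own wound progress, so a working sock would lead more active subjects to guess active. Or the blind could leak: the socks carry a fixed A or B code that research staff record. In either case a reporting effect would be added to any true quality-of-life effect, and the planned data could not separate the two, because no scheduled DFS-SF precedes the guess.

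The documents give no reason for the order. The guess can be collected just as well after the questionnaire.

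**Working it through.** The plan states no figure on this point, so the check is a reading of the procedures, followed by a bound on size that rests on assumptions.

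**1. Is the list a sequence?** Steps 12 and 13 are consecutive. Step 5 of the same list routes subjects by step number, which supports reading it in order. Nothing elsewhere places the DFS-SF before the guess.

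**2. Who follows this order?**
- Wound still open at week 12: steps 11, 12, 13, so pain, then guess, then DFS-SF.
- Wound closed before week 12: the subject performs the EOS evaluation at closure, so the same order applies.
- Wound found closed at Visit 12/EOS: the step 5 range of 7 to 12 takes in the guess (12) and leaves out the DFS-SF (13). The subject is then sent to the Wound Closed entry, which calls for the EOS evaluation. The guess still comes first, but the text does not make clear when the DFS-SF is given.

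**3. What is exposed?** The DFS-SF has 5 + 5 + 5 + 10 + 4 = 29 items, all self-rated. VAS pain is at step 11, before the guess, so the order does not touch it.

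**4. How large could the effect be?**

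Bias in the between-arm difference = (score shift caused by asking the guess first, between those who believe active and those who do not) × (difference between arms in the share who believe active).

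The documents give neither factor. With assumed shifts of 0.1 to 0.3 SD and assumed belief gaps of 10 to 40 percentage points:

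- lower end: 0.1 × 0.10 = 0.01 SD
- upper end: 0.3 × 0.40 = 0.12 SD
- equal belief in both arms: shift × 0 = 0

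Only the part of the shift that comes from asking first counts. Whatever effect belief has without being asked is there under either order.

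**The case against.** **The order is not stated to be binding.** No sentence says that step 12 has to precede step 13. Where timing matters, the same list says so, as for imaging straight after sock removal in step 4. The baseline list lets SPP and tcpO2 be done at other visits. This stands: the claim is about the listed order. A reader might infer that subjects are required to declare their guess aloud to staff immediately before the questionnaire. The text says only that the subject is asked, and gives no mode of answer.

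**No leak of the blind is shown.** The control sock is described as visually identical, the trial is subject and evaluator blinded, and earlier studies are reported to show no significant skin-temperature difference. This also stands. Priming is a plausible mechanism that the documents do not demonstrate.

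**An inflated error rate does not follow.** A reader might turn the bias into a false-positive rate. With the standard error of a standardised difference equal to 2/√N, it is 2/√254 = 0.1255 at 254 subjects and 2/√2500 = 0.04 at 2,500. A 0.05 SD bias would then move a one-sided 2.5% test to P(Z > 1.96 − 0.05/0.1255) = 5.9% and P(Z > 1.96 − 0.05/0.04) = 24%. The documents do not support quoting these figures:
- The 0.05 SD is assumed. Over 0.01 to 0.12 SD the same formula gives 3.0% to about 16% at 254 and 4.4% to about 85% at 2,500, which is too wide to inform.
- If belief differs because the sock heals wounds, the DFS-SF is unlikely to be null, and false positive is the wrong name.
- 2,500 is a ceiling reached only through sample size re-estimation.
- Section 4 names no specific test for the DFS-SF and keeps it outside the hierarchy.

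**Moving the DFS-SF ahead of the wound assessment is a separate preference.** Items such as worry about healing properly reflect the state of the wound, so knowing the closure result is not a flaw of the same kind.

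**Conclusion.** The point holds as a low-priority improvement. As listed, the arm guess comes directly before the trial's self-rated quality-of-life endpoint, which is collected only at EOS. If belief differs between arms, the order could add a reporting bias to the DFS-SF comparison.

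The conclusion rests on two assumptions: that staff follow the listed order, and that stating a belief shifts later answers. The size is not known from the documents; the 0.01 to 0.12 SD range illustrates assumed inputs and is not an estimate.

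A reader might infer a threat to the trial's confirmatory claims. There is none: DFS-SF is not in the hierarchy, StO2 and closure are not questionnaire answers, and VAS pain is listed ahead of the guess. The change would alter no sample size, alpha or power figure.

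**What to change.** In Study Visit 12/EOS, swap steps 12 and 13: the DFS-SF becomes step 12 and the arm guess step 13, after all patient-reported measures.

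Update step 5 at the same time. Its range of 7 to 12 now includes the guess and omits the DFS-SF. After the swap alone it would do the reverse. Extending it to 7 to 13 covers both. The Wound Closed entry should then make clear whether the EOS evaluation it calls for repeats them, so that each subject's DFS-SF has one defined time and precedes the guess.

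The cost is an edit to two step numbers and one range, with no added patients, data or visit time.
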